**B. Exploratory Objective 2: Assessment of tumor response using alternative radiologic criteria**

Rationale:

Sarcomas often display atypical radiographic changes in response to treatment. Traditional size-based criteria, such as RECIST and WHO criteria, in musculoskeletal tumors have been shown to be relatively insensitive to biological response as measured by other markers, such as histologic necrosis. This is probably due the tendency of sarcomas to undergo internal hemorrhage and necrosis, and as a result enlarge in size (pseudoprogression) despite the fact that the tumor is actually exhibiting positive treatment response. Comparable findings have been reported in other large STS treated with pazopanib. With current advances in radiographic imaging, tumor responses or progression can be detected much earlier, and eliminate some of the clinical problems with RECIST. Additionally, tumor response to immunotherapy often shows initial increase in size, followed by stabilization and shrinkage.

While the official endpoint for this study is still RECIST 1.1, we are including alternative radiologic criteria and techniques to aid in developing the best imaging modality for subsequent trials utilizing immunotherapy for sarcomas.

Approach:

A. Analysis of CT imaging using Choi Criteria and Immune-Related Response Criteria

Subjects enrolled on this study will undergo CT imaging for tumor imaging as per the guidelines of RECIST 1.1 and as detailed in the protocol. In addition to standard tumor measurements performed by the investigators, a blinded radiologist will analyze tumor response by published Choi criteria and immune-related response criteria.

**Modified CT Response Evaluation Criteria (Choi criteria)**

Tumor size is measured in the longest cross-sectional dimension for each lesion at each time point. As in RECIST criteria, the sum of the longest dimensions of selected target lesions are measured, and the absolute and percent changes of the sum from the pretreatment evaluation to subsequent evaluations are calculated.

Response	Definition
CR	
 
• Disappearance of all lesions
 
• No new lesions
 

PR	
 
• A decrease in size of <math>\geq 10\%</math> or a decrease in tumor density (Hounsfield units) <math>\geq 15\%</math> on CT
 
• No new lesions
 
• No obvious progression of nonmeasurable disease
 

SD	
 
• Does not meet the criteria for CR, PR, or PD
 
• No symptomatic deterioration attributed to tumor progression
 

PD	
 
• An increase in tumor size of <math>\geq 10\%</math> and does not meet criteria of PR by tumor density (Hounsfield units) on CT
 
• New lesions
 
• New intratumoral nodules or increase in the size of the existing intratumoral nodules
 

**Table F3: Modified CT Response Criteria (Choi criteria).** Taken from Choi et al. J Clin Oncol, 2007. 25(13): 1753-1759

Immune-related Response Criteria	

At the baseline tumor assessment, the sum of the products of the two largest perpendicular diameters (SPD) of all index lesions (up to 5 lesions per organ, up to 10 visceral lesions) is calculated. At each subsequent assessment, the SPD of the index lesions and of new, measurable lesions (<math>\geq 5 \times 5</math> mm, up to 5 new lesions per organ, up to 10 visceral lesions) are added together to provide the total tumor burden:
 
Tumor burden = SPDindex lesions + SPDnew, measurable lesions
	
Response	Definition
irCR	
 
• Complete disappearance of all lesions (whether measurable or not)
 
• No new lesions
 
• Confirmation by a repeat, consecutive assessment no less than 4 weeks from the date first documented
 

irPR	
 
• Decrease in tumor burden by <math>\geq 50\%</math> relative to baseline confirmed by a consecutive assessment at least 4 weeks after first documentation
 

irSD	
 
• Not meeting criteria for irCR or irPR in absence of irPD
 

irPD	
 
• Increase in tumor burden <math>\geq 25\%</math> relative to nadir (minimum recorded tumor burden)
 
• Confirmation by a repeat, consecutive assessment no less than 4 weeks from the date first documented
 

**Table F4: Immune related response criteria.** Adapted from Wolchok et al, Clin Cancer Res 2009, 15(23): 7412-20

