### 1.5 Rationale for Expansion Cohort in Alveolar Soft Part Sarcoma

We have completed accrual of the first 30 patients in this study, including 12 patients with ASPS. Out of 10 evaluable patients, all of whom enrolled on study with progressing disease, 5 patients achieved partial response, and 2 patients achieved minor responses and remain on study therapy. One patient had PD at 3 months and withdrew consent at that time. One patient progressed prior to 3 month imaging. Two patients progressed after the 3 month timepoint. One patient was discontinued for axitinib-related toxicity. The final patient has not yet reached 3 month assessments.

Based on the significant and largely durable responses in ASPS patients, we will expand the study to enroll up to 10 additional patients to obtain additional data regarding safety and efficacy.

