### 3.3 Exploratory endpoints

- The quantity of CD3+ T-cells in peripheral blood and in tumor biopsies at each timepoint (baseline, cycle 3, and off-study).
- The expression category in tumor tissue (none (0%), low (<5%), intermediate (5-50%), or high (>50%) of PD-1, PD-L1, PD-L2, CTLA-4, TIM-3, LAG-3 at each timepoint (baseline, cycle 3, and off-study).
- The following T cell subsets will be studied in peripheral blood and tumor tissue: (CD4, CD8, T-reg, CTLA4, TIM3, LAG3, memory, naïve, PD-1, Ki67). For each subset, the absolute change in the relevant marker(s) value will be calculated:
  - Cycle 3 marker value minus Baseline marker value
  - Off-study marker value minus Cycle 3 marker value
  - Off-study marker value minus Baseline marker value

Evaluable criteria:

Eligible subjects who receive at least one cycle of each study drug, and successfully undergo at least one post-treatment core biopsy and blood draw.

- Utilizing each of the alternative (non-RECIST) radiological criteria we will categorize clinical benefit status (CR/PR/SD vs PD). CT and/or MRI with dynamic contrast enhanced sequences will be collected throughout the study at every disease evaluation and analyzed using Choi criteria, MRI volumetrics, and immune-related response criteria. PET/CT will be obtained at baseline, Cycle 3, and off-study and tumor response determined by PERCIST 1.0.

Evaluable criteria:

Eligible patients who receive at least one cycle of each study drug and undergo at least one post-treatment radiographic imaging study.

- The quantity of circulating tumor cells (CTCs) in peripheral blood will be measured at three timepoints: 1. Baseline, 2. Cycle 3, and 3. Off-study.

Evaluable criteria:

Eligible patients who receive at least one cycle of each study drug and undergo at least one post-treatment blood sampling.

- RNA expression of a panel of angiogenesis and immune related genes in tumor biopsies and peripheral blood samples. Expression profiles will be obtained at baseline and at Cycle 3 Day 1 on treatment.

Evaluable criteria: Eligible patients who receive at least one cycle of study drug and undergo at least one post-treated radiographic imaging study.

- T cell clonality indices in tumor and peripheral blood obtained at baseline and at Cycle 3 Day 1.

Evaluable criteria: Eligible patients who receive at least one cycle of study drug and undergo at least one post-treated radiographic imaging study.

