### 12.5 Follow-up Evaluations

After treatment completion the following assessments should be performed at least **every 3 months (or every 12 weeks)** ( $\pm 7$  days) or as clinically indicated, as per standard of care.

Patients without documented evidence of objective disease progression will continue to have the same **imaging studies** as used at Baseline and during Treatment, performed at a 12-week interval during Follow-up, until disease progression.

Follow-up Visit: The following assessment(s) must be performed during Follow-up.

- *Adverse events: (Any SAE, or follow up to a SAE, including death due to any cause other than progression of the cancer under study that occurs to any subject from the time the consent is signed through **90 days** following end of treatment, or the initiation of new anti-cancer therapy, whichever is earlier, whether or not related to the Merck product, must be reported within 24 hours to the Sponsor and within 2 working days to Merck Global Safety. All subjects with SAEs must be followed up for outcome. (See Section 15.0 and Appendix A for details).)*
- PE
- ECOG PS
- Weight
- V/S (BP, HR, RR, oral temp and O2 saturation)
- CBC (with differential and platelets)
- CMP, Mg, Phosphate, direct bilirubin
- Coagulation factors (PT/INR, aPTT)
- TFTs (T3, T4 and TSH)
- Urine Pregnancy Test
- U/A (if protein 2+ or greater (grade 2) with no evidence of infection or contaminated sample, obtain urine microalbumin and urine creatinine clearance)
- 2D ECHO: only if clinically indicated
- 12-Lead ECG, only if clinically indicated

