#### Endpoints

The primary endpoint will be the progression-free survival by RECIST 1.1 in evaluable patients treated with combination axitinib/pembrolizumab.

The secondary endpoints include:

- The objective response rate (ORR) is defined as the proportion of patients whose response by RECIST 1.1 is complete response (CR) or partial response (PR). The clinical benefit rate (CBR) is the proportion of patients whose response by RECIST 1.1 is complete response (CR), partial response (PR), or stable disease (SD). The time to progression (TTP) is defined as time from treatment initiation to first occurrence of progression by RECIST v1.1 or death of sarcoma patients treated with concurrent axitinib/pembrolizumab therapy. Overall survival (OS) is defined as the elapsed time from treatment initiation to death from any cause, whichever is earlier. Patients alive or those lost to follow-up will be censored at the last date of contact (or last date known to be alive).
- Adverse events, including dose-limiting toxicity and grade 3 or grade 4 serious adverse events
  - DLT includes treatment-related (possible, probably, or definite) grade 3 or higher toxicities as detailed in section 7.2. Toxicity will be reported by short name, type, grade, and attribution as per CTCAE v4.0.3.

The exploratory endpoints include:

- The quantity of CD3+ T-cells in peripheral blood and in tumor biopsies at each timepoint (baseline, cycle 3, and off-study).
- The expression category in tumor tissue (none (0%), low (<5%), intermediate (5-50%), or high (>50%) of various markers including PD-1, PD-L1, PD-L2, CTLA-4, TIM-3, LAG-3 at each timepoint (baseline, cycle 3, and off-study).
- The following T cell subsets will be studied in peripheral blood and tumor tissue: (CD4, CD8, T-reg, CTLA4, TIM3, LAG3, memory, naïve, PD-1, Ki67). For each marker, the absolute change in the marker(s) value will be calculated:
  - Cycle 3 marker value minus Baseline marker value
  - Progression marker value minus Cycle 3 marker value
  - Progression marker value minus Baseline marker value
- For each of the alternative (non-RECIST) radiological measurements we will categorize tumor response as CR/PR/SD vs PD. CT and/or MRI with dynamic contrast enhanced sequences will be collected throughout the study at every disease evaluation and analyzed using Choi criteria, MRI volumetrics, and

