We will describe the relationship between the assessment of tumor response according to RECIST 1.1 and tumor response according to alternative radiologic methods (CT-based Choi criteria, immune related response criteria, MRI volumetrics, and PERCIST 1.0) using a 2 x 2 table to estimate the concordance between the two approaches. Results will be reported with 95% confidence interval on the proportion concordant. We are not attempting to demonstrate superiority of the alternative approaches, thus we will not use McNemar's test. We simply will describe the relationships between the approaches.

To test for the association of absolute change in CTC counts at two time points (cycle 3 and off-study) compared to baseline with clinical benefit status (CR/PR/SD vs. PD), we will use a Student t-test and Wilcoxon rank sum test for a specific time point and analysis of variance (ANOVA) and Kruskal-Wallis test for comparing all two time points. Repeated measure data analysis method will be used to analyze CTC count profiles by clinical benefit status.

To test for the association of absolute change in CTC counts at two time points (cycle 3 and off-study) compared to baseline with progression-free status at 3 months (progression vs. no progression), we will use a Student t-test and Wilcoxon rank sum test for a specific time point and analysis of variance (ANOVA) and Kruskal-Wallis test for comparing all two time points. Repeated measure data analysis method will be used to analyze CTC count profiles by progression-free status at 3 months.

Developing candidate biomarkers: We will be obtaining a large number of variables and looking for associations with response. In parallel to the above analysis, we will also utilize penalized logistic regression with bootstrapping to identify variables associated with response. We will adjust for multiple testing using Bonferroni adjustment and false discovery rate (FDR) due to multiplicity.

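### A patient with immune-related progression and no later confirming scan is classed as irSD under Table F4, and so counts as clinical benefit in the irRC-versus-RECIST table

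*Combined protocol and SAP*

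**What the plan says.** Table F4 (Appendix F, part B) sets irPD at a rise in tumor burden of at least 25% from nadir and adds a confirmation requirement: "Confirmation by a repeat, consecutive assessment no less than 4 weeks from the date first documented". irSD is whatever remains: "Not meeting criteria for irCR or irPR in absence of irPD". The table has no unconfirmed or not-evaluable category.

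Section 16.2 reduces each alternative criterion to two classes: "we will categorize tumor response as CR/PR/SD vs PD". Section 16.3 then compares each with RECIST 1.1 "using a 2 x 2 table to estimate the concordance between the two approaches", with a 95% confidence interval on the proportion concordant. Section 3.3 sets the evaluable set: "Eligible patients who receive at least one cycle of each study drug and undergo at least one post-treatment radiographic imaging study". One post-treatment scan is therefore enough.

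On scans after progression, the documents say:

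- Section 12.3 and footnote A of the Section 12.7 calendar waive off-treatment CT/MRI when the patient came off for radiographic progression.
- Section 12.5 ties follow-up imaging to patients who have not progressed ("Patients without documented evidence of objective disease progression will continue to have the same" imaging as before, until progression).
- Section 8.9 sets a telephone call as the minimum contact after confirmed progression.
- Section 11.0 schedules a confirmatory scan at 6 weeks for patients who stay on study despite RECIST progression.
- Section 14.1 says that response assessments after progression keep the 12-week frequency. The same paragraph limits re-evaluation of off-treatment patients to the period before documented progression.

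**The concern.** RECIST PD counts at the first scan that shows it, whereas irPD needs a second scan. A patient who stops at progression and is not scanned again meets the first definition but cannot meet the second. Because irSD is the residual category, the missing scan becomes a favorable classification.

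The comparison of response criteria is meant to inform the design of later sarcoma trials (Section 1.7.2). Section 16.3 plans no test of superiority, so the concordance proportion and the pattern of its off-diagonal cells are the result. Patients in the RECIST PD / irRC benefit cell would look like progressions that irRC avoided calling, when some of them were only not rescanned. The planned confidence interval reflects sampling error and would not show this.

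**Working it through.** The plan states no target or power for this concordance, so there is no figure to reproduce. The check traces the definitions and then gives an illustration.

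**Step 1. One patient through the rules.** The first post-baseline scan shows RECIST PD and a burden rise of at least 25%. Treatment stops and no CT/MRI follows.

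- RECIST 1.1: PD.
- irCR, irPR: not met.
- irPD: threshold met, confirmation absent, so not met.
- irSD: met as the residual.
- Evaluable under Section 3.3: yes.
- 2 x 2 cell: RECIST PD, irRC benefit, so discordant.

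**Step 2. Would RECIST PD usually reach the irRC threshold?** RECIST PD by target growth needs a 20% rise in summed diameters. irRC uses products of two diameters. If both diameters grow equally, the lesions are the same and the nadirs coincide, 1.2² = 1.44. That is a 44% rise, above 25%. PD called on small new lesions need not reach 25%.

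**Step 3. Direction.** An unconfirmed irCR or irPR also drops to irSD, but stays on the benefit side. Only an unconfirmed irPD crosses the dividing line.

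**Step 4. Who is affected.** Section 16.3 does not say whether the table uses best response or a time point. With best response (Section 14.1.4), patients who had SD, PR or CR before progressing are benefit under RECIST as well. The artefact then falls mainly on patients whose best RECIST response is PD.

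**Step 5. Size, as an illustration.** Assumptions, none of them a finding of the plan for this analysis:

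- N = 40 with irRC reads (the planned evaluable number in Section 16.4).
- A fraction d = 0.60 with RECIST PD (the complement of the 40% 3-month PFS in Section 16.4).
- Perfect agreement if every patient were rescanned.
- A share s of progressors without a confirming scan.

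Concordance = 1 − d × s. Progressors: 40 × 0.60 = 24. Each misclassified patient costs 1/40 = 2.5 points.

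| s | Misclassified | Concordant | Concordance | Exact 95% CI |
|---|---|---|---|---|
| 0 | 0 | 40/40 | 100% | 91.2% to 100% |
| 25% | 6 | 34/40 | 85% | 70.2% to 94.3% |
| 50% | 12 | 28/40 | 70% | 53.5% to 83.4% |
| 100% | 24 | 16/40 | 40% | 24.9% to 56.7% |

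With 16 progressors (d = 40%), s = 50% gives 32/40 = 80% and s = 100% gives 24/40 = 60%. With 32 progressors (d = 81%, the complement of the 19% null rate, rounded to whole patients), s = 50% gives 24/40 = 60% and s = 100% gives 8/40 = 20%.

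**The case against.** **Section 14.1 asks for assessments after progression.** A scan 12 weeks later would satisfy the 4-week minimum, so a reader should not infer that the documents provide no further scan at all. This stands. The accurate statement is that Section 14.1 conflicts with Sections 8.9, 12.3 and 12.5, and with its own limit on off-treatment patients. Section 12.3 also lists an off-treatment PET/CT without the progression waiver, and Section 14.1.3 lets a diagnostic-quality CT component serve for RECIST measurement. That is a possible source of confirmation, but the plan assigns PET/CT to PERCIST, and only patients positive at baseline have it.

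**irSD is not stated as an analysis rule for these patients.** Section 16.3 is silent, and a statistician could code them not evaluable. That is possible, but Table F4 has no such category and its wording places them in irSD. A choice that changes the result should be made in advance.

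**The illustration sits at the high end.** This stands. PFS failures include deaths (Section 14.2), and patients without a post-treatment scan are outside this analysis. Not every RECIST PD carries a 25% rise. irRC is planned for patients followed by CT (Section 1.7.2), so N may be below 40. Some discordance is genuine, because irRC adds new measurable lesions to the burden instead of calling PD. Patients kept on study do get the 6-week scan.

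**It is one of four exploratory, descriptive comparisons.** True, and no decision rule depends on it.

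**Conclusion.** The point holds as a defect in the classification rule. As written, an unconfirmed and unrescanned irPD becomes irSD and enters the benefit cell. The resulting bias runs only toward RECIST PD / irRC benefit. The visit schedule makes such patients likely, and the sections on imaging after progression contradict each other.

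The per-patient effect is 2.5 points at N = 40. The 85%, 70% and 40% figures hold only under the assumptions in the working. The share of progressors without a confirming scan is not in the documents, so the total bias is unknown.

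Two stronger readings are not supported. A reader might take the patient in Section 1.5 ("One patient had PD at 3 months and withdrew consent at that time") as a proven instance. That section gives neither the burden change, nor the imaging method, nor whether a later scan exists, so the case is consistent with the problem but does not demonstrate it. A reader might also take 24 of 40 as the expected number affected. That would need every 3-month PFS failure to be a scanned progression with a rise of at least 25% and no rescan.

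The primary and secondary efficacy endpoints use RECIST 1.1 and are untouched. The change is worth making because it is cheap and the comparison is intended to guide later trials.

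**What to change.** 1. In Table F4 and Section 16.3, define a rise of at least 25% from nadir with no later scan before new therapy as *unconfirmed irPD*, and state that it is not coded irSD.
2. Report the number of such patients.
3. Give the irRC-versus-RECIST concordance twice: once with them counted as irPD and once with them excluded as not evaluable. Neither version alone is enough. Counting them all as irPD removes the confirmation step that distinguishes irRC and pushes agreement with RECIST upward.
4. Reconcile Section 14.1 with Sections 8.9, 12.3 and 12.5 on assessments after progression.

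The cost is a few sentences and one extra table. No new scans are needed. The downside is that some pseudoprogressions without a later scan are counted as irPD in one of the two versions.

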## B. Dynamic Contrast Enhanced Magnetic Resonance Imaging (DCE-MRI)

Subjects enrolled in this study will undergo an MRI scan as per the research protocol. All imaging will be performed on a 3T Skyra magnet (Siemens, Erlangen, Germany). A multiparametric MRI protocol containing conventional MR sequences will be obtained (including non-fat-suppressed T1 weighted, T2 weighted with fat saturation, and fat-saturated pre- and post-contrast T1 weighted images). Additional functional MRI techniques will be acquired, including diffusion-weighted imaging (DWI), magnetic resonance elastography (MRE), and dynamic contrast-enhanced MRI (DCE). The DWI sequences require approximately 5 minutes for acquisition; the MRE requires approximately 10 minutes for acquisition; the DCE sequences require approximately 5 minutes for acquisition. Formal reports for these exams will be generated by the co-investigators, and images will be stored in PACs. The MRI lasts approximately 45-60 minutes.

Images will be analyzed using third party software (iNtuition, TeraRecon, Foster City, California). Changes in index tumor size will be assessed using conventional size-based RECIST 1.1 criteria; in addition, semi-automated tumor segmentation will be performed for volumetric analysis of changes in tumor size. Apparent diffusion coefficient (ADC) maps will be constructed using the scanner's in-line software (Syngo MapIt, Siemens, Erlangen, Germany) to quantify restricted diffusion. Regions of interest will be constructed on ADC maps for comparison of ADC values; tumor volumetric segmentation on ADC map will also be performed for analysis of whole-tumor composition.

Enhancement characteristics will be analyzed according to modified Choi criteria applied to subtracted post-contrast sequences, with partial response (PR) defined as a decrease  $\geq 10\%$  in tumor size or a decrease  $\geq 15\%$  in tumor contrast enhancement; progression (PD) as new lesions, an increase  $\geq 10\%$  in tumor size without meeting any criteria for a PR according to tumor contrast enhancement, or an increase  $\geq 15\%$  in tumor contrast enhancement. Complete response (CR) will be defined as complete disappearance of all lesions and no new lesions; stable disease will be defined as tumor not meeting criteria for CR, PR, or PD.

DCE-MRI perfusion kinetics will be calculated for the index tumor. Tumor firmness will be assessed based on the shear modulus derived from MRE. Comparisons of pre- and post-treatment changes in tumor size, enhancement characteristics, ADC values, and tumor elasticity will be performed using paired t-tests and McNemar's test as appropriate.

